7.5. Concomitant Therapy

No other chemotherapy, radiotherapy, immunotherapy, cancer-related hormone therapy, or experimental drugs will be permitted while the patients are on this study. The need for any form of radiotherapy will be cause for early discontinuation from study treatment (palliative radiotherapy is permitted if clinically indicated, after discussion with the Lilly CRP/CRS). In addition, any disease progression requiring other forms of specific antitumor therapy will also necessitate discontinuation from study treatment. Appropriate documentation for all forms of premedications, supportive care, and concomitant medications must be captured on the eCRF. Replacement hormonal therapy initiated before study entry will be allowed.

Patients should receive full supportive care with the exception that the routine use of G-CSF is not permitted during this study. Patients should not receive G-CSF prophylactically in any cycle. G-CSFs may only be used for patients who have ANC<0.5 × 10⁹, neutropenic fever, or documented infections while neutropenic. G-CSFs must be discontinued at least 24 hours before the start of the next cycle of treatment. Should the use of hematopoietic colony-stimulating factors (CSFs) be necessary, follow the American Society of Clinical Oncology (ASCO) recommendations for the use of CSFs (Smith et al. 2006). If clinically indicated at any time during the study, erythropoietin and packed red blood cell transfusions may be used according to ASCO guidelines (Rizzo et al. 2008).

All concomitant medications should be recorded throughout the patient's participation in the study.

7.5.1. *Supportive Care Guidelines for Olaratumab*

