10.8. Efficacy

The following endpoints will be listed and summarized: individual best overall response (BOR) using RECIST version 1.1 criteria, DOR, PFS, and OS. In addition, the following endpoints will be listed and summarized using irRECIST criteria: BOR, DOR, and PFS by irRECIST. Rates including ORR and DCR will be computed and the estimates will be reported with exact 95% CIs. Time-to-event variables including PFS, DOR, and OS will be analyzed using the Kaplan-Meier method (Kaplan and Meier 1958). Survival curves will be used to summarize the data. If data are sufficiently mature, medians will be reported with the 95% CIs. In addition, for each time-to-event variable, survival rates at adequate time points will be reported (for example, 3, 6, and 12 months).

Individual changes in the tumor size over time will be presented graphically using line plots. The change in tumor size corresponding to the best response based on target lesions for each patient will be represented in waterfall plots by cohort.

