- Cystic lesions thought to represent cystic metastases can be considered as measurable lesions, if they meet the definition of measurability. If noncystic lesions are presented in the same patients, these are preferred for selection as target lesions.

Lesions with Prior Local Treatment:

- Tumor lesions situated at a previously irradiated area, or in an area subjected to other loco-regional therapy, are non-measurable unless there has been demonstrated progression in the lesion.

Baseline Documentation of Target and Non-Target Lesion

Target Lesions

When more than 1 measurable lesion is present at baseline, all lesions up to a maximum of 5 lesions total (and a maximum of 2 lesions per organ) representative of all involved organs should be identified as target lesions and will be recorded and measured at baseline. Non-nodal Target lesions should be selected on the basis of their size (lesions with the longest diameter), be representative of all involved organs, and can be reproduced in repeated measurements..

Measurable lymph nodes are target lesions if they meet the criteria of a short axis of ≥ 15 mm by CT scan. All measurements are to be recorded in the case record form (CRF) in millimeters (or decimal fractions of centimeters [cm]).

Nontarget Lesions

All other lesions (or sites of disease) are identified as nontarget lesions (chosen based on their representativeness of involved organs and the ability to be reproduced in repeated measurements) and should be recorded at baseline. Measurement of these lesions are not required but should be followed as 'present,' 'absent,' or in rare cases 'unequivocal progression.' In addition, it is possible to record multiple nontarget lesions involving the same organ as a single item on the CRF (for example, multiple liver metastases recorded as one liver lesion).

Lymph nodes with short axis ≥ 10 mm but < 15 mm should be considered nontarget lesions. Nodes that have a short axis < 10 mm are considered nonpathological and are not recorded or followed.

Specifications by Methods of Measurement

All measurements should be recorded in metric notation, using a ruler or calipers if clinically assessed. All baseline evaluations should be performed as closely as possible to the beginning of treatment and never more than 4 weeks before the beginning of the treatment.

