The best overall response is the best response recorded from the start of the study treatment until the earliest of objective progression or start of new anticancer therapy, taking into account any requirement for confirmation. The patient's best overall response assignment will depend on the findings of both target and nontarget disease and will also take into consideration the appearance of new lesions. The Best Overall Response will be calculated via an algorithm using the assessment responses provided by the investigator over the course of the trial.

Time Point Response

It is assumed that at each protocol-specified time point, a response assessment occurs. (When no imaging/measurement is done at all at a particular time point, the patient is not evaluable (NE) at that time point.) Table ATT.8.1 provides a summary of the overall response status calculation at each time point for patients who have *measurable disease* at baseline.

Table ATT.8.1. Time Point Response: Patients with Target (\pm Nontarget) Disease

Target Lesions	Non-Target Lesions	New Lesions	Overall Response
CR	CR	No	CR
CR	Non-CR/non-PD	No	PR
CR	Not evaluated	No	PR
PR	Non-PD or not all evaluated	No	PR
SD	Non-PD or not all evaluated	No	SD
Not all evaluated	Non-PD	No	NE
PD	Any	Yes or No	PD
Any	PD	Yes or No	PD
Any	Any	Yes	PD

Abbreviations: CR = complete response; NE = not evaluable; PD = progressive disease; PR = partial response; SD = stable disease.

Table ATT.8.2 is to be used when patients have *nonmeasurable* disease only.

Table ATT.8.2. Time Point Response: Patients with Nontarget Disease Only

Nontarget Lesions	New Lesions	Overall Response
CR	No	CR
Non-CR/non-PD	No	Non-CR/non-PD ^a
Not all evaluated	No	NE
Unequivocal PD	Yes or No	PD
Any	Yes	PD

Abbreviations: CR = complete response; NE = not evaluable; PD = progressive disease.

^a non-CR/non-PD is preferred over SD for nontarget disease.

Frequency of Tumor Re-Evaluation

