6.10. Concomitant Therapy

All medications will be coded to the generic preferred name according to the current World Health Organization (WHO) drug dictionary. All concomitant medications listings will include both the term reported in CRF and the WHO dictionary term and if concomitant medication use is due to an adverse event (AE), the associated AE will also be listed.

Prior anti-cancer systemic therapy, radiotherapy and surgery will be summarized. Summaries will include the reason, type of therapy, number of prior regimens and drug name. Prior therapies will also be listed, including the patients response to prior therapy.

Anti-cancer systemic therapy, radiotherapy or surgery that occurs post discontinuation of study treatment is captured separately from concomitant medication as the existence of such

therapies can lead to censoring of time to event endpoints. Patients that received post discontinuation therapies will be listed and summarized.

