6.11. Efficacy Analyses

6.11.1. Efficacy Definitions

The following definitions for efficacy endpoints will be used:

Overall response rate (ORR) is the proportion of patients who achieved a complete response (CR) or partial response (PR) out of all patients treated. Tumor responses will be measured and recorded using the appropriate guidelines [RECIST 1.1 (Eisenhauer et al. 2009)].

Best response is determined as the best response recorded from start of study treatment until PD or recurrence.

Disease Control Rate (DCR) is the proportion of patients who achieved a best response of complete response (CR), partial response (PR) or stable disease (SD) out of all patients treated.

Immune-related objective response rate (irORR) is defined as the proportion of treated patients achieving a best overall response of PR or CR per irRECIST, particularly, the best overall response by irRECIST closely related to confirmed response by RECIST. Immune-related ORR further captures responses after unconfirmed PD and does not require confirmation. For example:

- If the best response by RECIST v.1.1 is CR, then the best response by irRECIST is CR.
- If the best response by RECIST v.1.1 is PR, SD, or PD, the best response by irRECIST is the best response over the initial assessment (prior to PD by RECIST v.1.1) and the confirmation stage.

Overall, the best response by irRECIST should be the same or better than the best response by RECIST v.1.1 criteria. In addition, patients who do not have any postbaseline tumor response assessments for any reason are considered non-evaluable and will be included in the denominator when calculating the response rate.

Immune-related disease control rate (irDCR) is defined as the proportion of treated patients achieving a best overall response of CR, PR or SD per irRECIST.

[figure not shown]
Duration of Response will be calculated for ORR and is defined only for responders (ie. CRs and PRs). It is measured from the date of first evidence of a confirmed response to the date of first progression of disease or the date of death due to any cause, whichever is earlier. For each patient who is not known to have died or to have had a progression of disease as of the data-inclusion cut-off date, duration of response will be censored at the date of last objective response assessment prior to the date of any subsequent systemic anticancer therapy.

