Duration of Stable Disease will be calculated only for patients with best response of stable disease, CR or PR. It is measured from the date of start of treatment to the date of first progression of disease or the date of death due to any cause, whichever is earlier. For each patient who is not known to have died or to have had a progression of disease as of the data-inclusion cut-off date, duration of stable disease will be censored at the date of last objective response assessment prior to the date of any subsequent systemic anticancer therapy.

[figure not shown]
Duration of response by irRECIST is defined from the date of first documented irCR or irPR (responder) to the date of irPD or the date of death due to any cause, whichever is earlier.

Graphic Example:

Scenario 1: The initial PD is confirmed at the next scan (consecutive PD). The efficacy variables by irRECIST and RECIST are the same.

Scenario 2: The initial PD is not confirmed at the next scan (non-consecutive PD). The efficacy variables by irRECIST and RECIST v.1.1 are different.

In addition, the best response after initial PD may be listed. Other efficacy analysis based on irRECIST may be performed for exploratory analysis.

Change in tumor size will be assessed in each patient with measurable disease using radiographic imaging. Tumor size is the sum of the tumor measurements for target lesions at each tumor evaluation. Change in tumor size is defined as the percent change in tumor size from

the baseline evaluation to the minimum post-dose evaluation. Other definitions of CTS may be explored (including specific time points, and AUC formulations).

Progression-free survival (PFS) time is defined as the time from the date of start of study treatment to the first date of PD (symptomatic or objective) or death due to any cause, whichever occurs first. For patients who are not known to have died or progressed as of the data-inclusion cut-off date, PFS time will be censored at the date of the last objective progression-free disease assessment prior to the date of any subsequent systemic anticancer therapy.

Immune-related progression-free survival (irPFS) is defined as the date from the treatment started date to the time of PD assessed by irRECIST.

- If the initial PD is confirmed, then the date of immune-related (ir)PD is the initial PD date by RECIST v.1.1.
- If the initial PD is unconfirmed, then the date of irPD is the date of second PD.

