6.11.2. Efficacy Analyses

Reported lesion data (target/ non-target), investigator assessment of response, duration of response/stable disease, PFS and OS will be listed for all patients.

Efficacy data will be summarized according to treatment. If data warrant, efficacy analyses of ORR and irORR will also be presented separately for each sarcoma histology and treatment.

The following efficacy summaries will be provided:

- ORR, DCR, irORR and irDCR will be presented with exact 95% CI.
- Time to event endpoints including PFS, DOR, irPFS, irDOR and OS will be summarized descriptively using the Kaplan-Meier method. Survival curves will be used to summarize the data. If data are sufficiently mature, medians will be reported with the 95% CIs. In addition, for each time-to-event variable, survival rates at adequate time points will be reported (for example, 3, 6, and 12 months).
- Change in tumor size over time will be presented graphically using line plots. Minimum change in tumor size will be presented using a waterfall plot.

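### SAP 6.11.1 omits Attachment 8's stop at new anticancer therapy; separately, no visible rule keeps shrinkage of a target lesion irradiated on study out of response rates and the waterfall plot (minor)

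*Protocol*

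**What the plan says.** **When best response ends.** SAP 6.11.1: "Best response is determined as the best response recorded from start of study treatment until PD or recurrence". Protocol Attachment 8 records best overall response "until the earliest of objective progression or start of new anticancer therapy". Both are current text, and the SAP sentence lacks the second limb.

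**Tumor size.** SAP 6.11.1 defines the change in tumor size as the percent change from "the baseline evaluation to the minimum post-dose evaluation", with no stop at progression or new therapy. SAP 6.11.2 then says: "Minimum change in tumor size will be presented using a waterfall plot". Protocol 10.8 plots something else: "The change in tumor size corresponding to the best response based on target lesions".

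**Radiotherapy on study.** Protocol 7.5 first makes radiotherapy a reason to stop study treatment and then allows a palliative exception: "The need for any form of radiotherapy will be cause for early discontinuation from study treatment (palliative radiotherapy is permitted if clinically indicated". The parenthesis adds that the sponsor's physician must be consulted. It does not limit the exception to non-target lesions.

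**Irradiated lesions.** Attachment 8 has one rule, placed with lesion measurability at baseline: "Tumor lesions situated at a previously irradiated area, or in an area subjected to other loco-regional therapy, are non-measurable", unless progression in the lesion has been shown. SAP 6.10 mentions "Anti-cancer systemic therapy, radiotherapy or surgery that occurs post discontinuation of study treatment", but only for therapy after discontinuation and only as a possible reason to censor time-to-event endpoints.

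**The concern.** There are two separate gaps, and both affect how antitumor activity is described.

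The first is a plain disagreement between the documents. A programmer following the SAP would keep counting assessments after new anticancer therapy starts; one following Attachment 8 would stop. The waterfall plot likewise has two definitions, and the SAP one takes the smallest value at any time after dosing.

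The second is an unhandled case. A patient may receive palliative radiotherapy to a target lesion, stay on study treatment and continue to be scanned. If the lesion shrinks, the target sum falls and the fall is credited to olaratumab plus pembrolizumab.

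In a single-arm, open-label trial, ORR, DCR, their irRECIST versions and the waterfall plot carry the description of activity, and the two Phase 1b interim analyses exist to look at it. Credit for radiation would push these results in the drugs' favour.

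**Working it through.** **Inputs.** N=31 (6 patients in Phase 1a plus 25 in Phase 1b at the recommended dose) and the Clopper-Pearson method come from Protocol 10.1.1. Exact 95% intervals for the rates come from Protocol 10.8 and SAP 6.11.2. A PR needs a fall of at least 30% in the target sum from baseline (Attachment 8). The number of patients irradiated on study is not given; I assume 1 to 3 falsely credited responders to show sensitivity.

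**1. The plan's own table.** Lower limit = 2.5% quantile of Beta(x, n−x+1); upper limit = 97.5% quantile of Beta(x+1, n−x). With n=31:

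| Cases | Computed limits | Table JGDQ.8 |
|---|---|---|
| 0 | 0 to 0.1122 | 0.0 to 0.11 |
| 5 | 0.0545 to 0.3373 | 0.05 to 0.34 |
| 10 | 0.1668 to 0.5137 | 0.17 to 0.51 |
| 15 | 0.3015 to 0.6694 | 0.30 to 0.67 |
| 20 | 0.4537 to 0.8077 | 0.45 to 0.81 |
| 25 | 0.6253 to 0.9255 | 0.63 to 0.93 |

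All six rows reproduce.

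**2. Can radiation alone give a PR?** Assume two target lesions of 50 and 40 mm. The 50 mm lesion is irradiated and falls to 20 mm; the other does not change. The sum goes from 90 to 60 mm: (60 − 90)/90 = −33.3%, a PR. The untreated lesion changed by 0%. In general, if the irradiated lesion is a share w of the baseline sum and the rest is stable, it must shrink by 0.30/w: 75% at w=0.4, 60% at 0.5, 50% at 0.6, 40% at 0.75 and 30% at 1.

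**3. Effect on ORR.** One patient is 1/31 = 3.2 points or 1/25 = 4.0 points. SAP 6.1 splits summaries by dose; in a six-patient dose level one patient is 1/6 = 16.7 points. Exact intervals at N=31:

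| Responders | ORR (95% CI) |
|---|---|
| 0 | 0% (0 to 11.2) |
| 1 | 3.2% (0.1 to 16.7) |
| 2 | 6.5% (0.8 to 21.4) |
| 3 | 9.7% (2.0 to 25.8) |
| 4 | 12.9% (3.6 to 29.8) |

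So one false responder on top of three true ones moves the estimate from 9.7% to 12.9%. DCR moves only if the patient had no CR, PR or SD before the radiotherapy.

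**4. Does another visible rule block it?**

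- The irradiated-lesion rule concerns baseline measurability.
- The not-evaluable category for target lesions covers an incomplete assessment or a changed method, not local treatment.
- Censoring of DOR, duration of stable disease and PFS in SAP 6.11.1 is triggered by systemic therapy only, and does not govern best response.
- Progression scans end at other anticancer therapy (Attachment 1, footnote c), but only for patients already off study treatment.
- Confirmation of response, where applied, does not help if the radiation shrinkage persists; irORR requires none.

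**5. Are the two gaps one problem?** No. Neither document says whether palliative radiotherapy counts as new anticancer therapy, so restoring the Attachment 8 wording would leave the radiotherapy case open.

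**The case against.** The strongest reply is that few patients could be exposed.

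- **New therapy.** Protocol 6.3.2 requires study drugs to stop before another effective agent is started. Attachment 1 asks for follow-up assessments before new therapy and ends scheduled progression scans once it begins. Few later scans would exist to enter best response.
- **Radiotherapy.** The 7.5 exception is case by case. False credit needs a treated target lesion, continued scanning, no earlier PD and enough shrinkage. SAP 6.11.1 also counts symptomatic PD for PFS, and its best-response sentence does not limit PD to objective PD. If symptoms of progression prompted the radiotherapy, the window may already be closed.
- **Governing text.** Attachment 8 belongs to a protocol approved in 2018, after the SAP of February 2017, and has best response calculated by algorithm. SAP 6.1 lets derivations follow updated sponsor standards.

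The first two replies stand as limits on frequency. They do not cover a painful target lesion irradiated without progression in a patient who continues treatment. The third does not settle the matter: no visible standard fills the gap, and the two definitions still differ in writing.

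A reader might go further and infer that the missing therapy stop is what lets radiation shrinkage count. Step 5 of the working shows it is not. A reader might also infer that irPFS is materially distorted, because irradiating the lesion behind a first PD could leave that PD unconfirmed. The clinical-stability conditions in Protocol 8.3 and Table ATT.8.3 take most such patients off treatment, so this route is rare.

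**Conclusion.** The point holds as a minor one. The SAP and Attachment 8 disagree on when best response ends, and the SAP and Protocol 10.8 disagree on the waterfall plot. Separately, the visible text would let radiation shrinkage of a target lesion count as PR or as the tumor-size minimum.

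The size is 3.2 points of ORR per affected patient at N=31, or 4.0 at N=25. The 1 to 3 patients used above (3.2 to 9.7 points) are an assumption, not an expected bias.

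The consequences are limited. The primary objective is safety, SAP 6.5 plans no hypothesis test, and Protocol 10.1.1 says its intervals are not decision criteria. OS is not affected, and radiotherapy after a first RECIST PD does not change RECIST PFS.

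The documents do not support a claim that no rule exists anywhere. The Attachment 1 comment on radiological assessment is redacted and the SAP's irRECIST graphic is not shown, so handling there cannot be excluded. The conclusion also rests on reading the 7.5 parenthesis as an exception to discontinuation, which is its natural sense.

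**What to change.** In SAP 6.11.1:

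- **(a)** End RECIST best response at the earliest of PD or start of new anticancer therapy, as in Attachment 8. End irRECIST best response and the tumor-size minimum at the earliest of irPD or start of new anticancer therapy; using irPD keeps responses after an unconfirmed first PD. State whether the waterfall plot shows that minimum or the Protocol 10.8 change at best response.
- **(b)** State that palliative radiotherapy under 7.5 falls under this rule and is not a stop under (a). From the date a target lesion is irradiated, later assessments do not count toward CR, PR, SD or the tumor-size minimum. Best response from before radiotherapy is kept, and PD can still be called. Radiotherapy to non-target lesions only leaves assessment unchanged.
- **(c)** List patients who received radiotherapy on study, since the SAP 6.10 listing covers only therapy after discontinuation.

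Dating irPD at first PD when the lesion behind it was irradiated before the confirmatory scan is at most a sensitivity analysis: it can call PD in a transient flare. Censoring PFS or DOR at radiotherapy is likewise optional, and SAP 6.3 already allows such analyses.

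The cost is a few SAP sentences and one listing. The date and site of on-study radiotherapy are needed; the CRF is not among the documents, so these may already be collected. The downside is that a patient whose untreated lesions respond only after radiotherapy gets no credit, so ORR may be slightly less favourable.

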7.5.1.1. Infusion-Related Reactions

As with other monoclonal antibodies, hypersensitivity reactions may occur during or following olaratumab administration. Premedications to be given prior to olaratumab infusions are described in Section [7.2.1](#).

An approximate 1-hour observation period is required after the administration of olaratumab during the first and second cycles of olaratumab. Patients should complete the olaratumab observation period prior to starting pembrolizumab (when applicable). If there is no evidence of an IRR during the initial 2 cycles of olaratumab, then no observation period is required for subsequent treatment cycles. In the event an IRR occurs thereafter, the 1-hour observation should be reinstated. During the observation period, patients treated with olaratumab should be closely monitored for signs and symptoms indicative of an infusion reaction by the medical staff from the start of the infusion until at least 1 hour after the end of the infusion in an area where emergency medical resuscitation equipment and other agents (epinephrine, prednisolone equivalents, etc.) are available.

Olaratumab infusion reactions will be defined according to the NCI-CTCAE Version 4.0 definition of IRRs.

Symptoms occurring during or following infusion of investigational therapy may also be defined according to AE categories such as allergic reaction, anaphylaxis, or cytokine release syndrome (NCI-CTCAE Version 4.0 section “Immune system disorders”). In the setting of symptoms occurring during or following infusion of investigational therapy, investigators are encouraged to use the AE term “infusion-related reaction” and any additional terms (including those not listed here) that best describe the event.

Treatment guidelines for olaratumab IRRs as well as premedications for subsequent infusions are described in [Table JGDQ.5](#).

Table JGDQ.5. Olaratumab Infusion-Related Reaction Treatment Guidelines

NCI CTCAE Grade	Treatment	Premedication at Subsequent Infusions
Grade 1 or 2	
Stop infusion and monitor symptoms. Additional appropriate medical therapy should be given according to standard medical practice; may include, but is not limited to:
 
 • Antihistamines (for example, diphenhydramine HCl) • Steroids (for example, dexamethasone) • Acetaminophen • Oxygen 
After recovery, the infusion rate should be decreased 50% for the duration of the infusion.
	Patients should be premedicated with antihistamines, steroids, acetaminophen, etc., as appropriate.
Grades 3 or 4	
Stop infusion. Administer immediate treatment. May include, but is not limited to:
 
 • Epinephrine • Bronchodilators and/or glucocorticoids for symptomatic bronchospasm • IV fluids and/or pressors for hypotension 
Treatment with olaratumab should be immediately and permanently discontinued.
	No subsequent dosing

All attempts should be made to obtain an anti-olaratumab antibody and olaratumab PK blood samples as close to the onset of the event as possible, at the resolution of the event, and 30 days (± 3 days) following the event. The procedure for sample collection and handling is described in a separate procedural manual.

Appropriate resuscitation equipment should be available in the room and a physician readily available during the period of drug administration.

Abbreviations: HCl = hydrochloride; IV = intravenous; NCI CTCAE = National Cancer Institute Common Terminology Criteria for Adverse Events.

